At the end of Year 2, the CAB and research team met to review all grouped suggestions gathered from the WGs and FGs. The CAB identified and integrated modifications or additions to our conceptual framework if needed based on the FG feedback. Next, the CAB reviewed the content, format, and learning objectives of each of the six PEI program modules and training protocol within the context of this finalized conceptual model. Specifically, the CAB identified the type of change needed (e.g., content, language, learning strategy), amount of change required (no change, small change, moderate change, large change), and barriers (timeline/budget). The CAB decided on the importance of the change (essential or non-essential), made final decisions on adaptations, and the physical adaptations of the PEI program materials were made by the developers of PEI as requested by the CAB.

Adapted PEI Program Intervention Evaluation (Phase 2; Clinical Trial)

In Year 3, The CAB worked with the research team to culturally adapt the intervention and identified two school counselors (i.e., an American Indian tribal member and a white non-tribal member) to provide it in the schools. Both providers completed the modified PEI program training based on CAB decisions for adaptation and the CITI Training (through Montana State University-Bozeman) before working with youth in the school. They also completed a background check for each school. Providers recorded youth attendance, dropout of the intervention, and completed the Brief Reactions Form for after each session.

In Year 3, we recruited 28 Native youth ages 8-12 years-old from the [two tribal serving school names] (15 youth per school) to participate in the adapted PEI program. The adapted PEI program was delivered to a group of 3-5 youths at one time with three groups participating in each school. Written informed consent was obtained from the parents or legal guardians before youth participated in the intervention or complete pre- and post-survey assessments. Youth participants also provided written assent before completing the pre-intervention and post-intervention surveys or participating in the adapted PEI program.

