Youth participants completed the pre-intervention survey (~30 minutes to complete based on our pilot study) one week before session 1 and the post-intervention survey one week after session 6 of the adapted PEI program. The post-adaptation usability survey was administered at the end of each session. Youth completed the survey using paper and pencil. The research team explained the purpose of the study and intervention. They also read the assent form out loud to youth and answered any questions youth had about the study. Those youth who verbally agreed and checked “yes” on the assent form completed the youth survey and participated in the intervention. Youth who choose not to participate in the study returned to their classroom. All youth were notified of their right to withdraw the study and intervention at any time without consequence. The research team helped youth who may have difficulty comprehending items or response options.

Youth Assessments. The CAB reviewed and approved the following instruments as being culturally appropriate (minor changes were made to existing measures) for our previous study

with 71 Native 8-13-years-old at the [tribal school name]. Each measure showed acceptable to excellent reliability and both convergent and discriminant validity with other established measures in that study (Scott, [name], Small, & McCullen, 2023).

Youth Demographics. We asked children to provide personal information including gender, age, ethnicity, tribal affiliation, grade level, and family structure.

Revised Child Anxiety and Depression Scales – Short Child Version (RCADS-SC).^{37,38} The RCADS-SC is a 25-item self-report instrument used to assess DSM-IV criteria (APA, 1994) of symptoms for anxiety disorders (excluding Posttraumatic Stress Disorder and Specific Phobias) and depression. We asked the children to rate how often each anxiety and depression symptom is true of them on a rating scale consisting of: 1 (Never), 2 (Sometimes), 3 (Often), and 4 (Always). Higher scores represent the experience of more anxiety and depression symptoms as based upon the DSM-IV criteria.

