We also will conduct individual interviews with 4 parents, 4 3rd-6th grade homeroom teachers, and the two providers of youth intervention participants. Youth will participate in the focus group on the last day of the intervention and parent/teacher/youth interviews will happen within a month of the last day of the intervention. Focus groups and interviews will be audio recorded.

Post-Intervention Acceptability Focus Group and Interview Procedure. We followed the same aforementioned general procedures for the focus groups. [name] and the project manager asked youth to describe what they liked about the adapted PEI program, which they thought was most useful, and whether it was appropriate for AI youth. They also asked for suggested improvements to content, material, and learning strategies. AI youth received a \$20 gift card for their participation.

Youth Post-Adaptation Usability Survey. Youth completed the identical usability survey³⁶ from the pre-adaptation phase at the end of each session. It assessed likability, acceptability, enjoyable, ease of learning and using skills, credibility, motivational appeal, perceived impact, and cultural appropriateness.

References

1. Evans-Campbell T. Historical trauma in American Indian/Native Alaska communities: A multilevel framework for exploring impacts on individuals, families, and communities. *Journal of interpersonal violence*. 2008;23(3):316-338.
2. Brown-Rice K. Examining the Theory of Historical Trauma Among Native Americans. *Professional Counselor*. 2013;3(3).

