- A. Informed Consent. The project manager will thoroughly review the consent form with the adult community stakeholder or parent/legal guardian either over the phone or in person, if needed. We have found that parents/legal guardians are more informed about the nature and purpose of the study when explained to them by tribal community member. The consent form will include a description of the non-adapted or adapted [PEI name] components, the types of questions being asked in the survey or work/focus group, and the risk and benefits of their child participating in the study. Adult community stakeholders will need to sign the written informed consent before participation is allowed in the work/focus groups. Parents/legal guardians will need to sign the written informed consent before youth participation is allowed in focus groups or adapted intervention.

The tribal research team member will thoroughly review the assent form with the youth at before the focus groups and pre-intervention survey assessment in a developmentally appropriate manner and ensure to the best of their ability that each youth understands the study's purpose, risks/benefits, and voluntary nature of the study (i.e., they can quit at any time or not answer questions without consequence). Tribal research team members will be required to successfully complete the CITI Social and Behavioral Research Best Practices training before working on the study. The assent form will provide a description of the adapted [PEI name] components, the types of questions being asked in the survey and focus group, and the risk and benefits of participating in the study using developmentally appropriate language for youth comprehension. They will make all attempts possible to help the students understand the nature of the study. Youth written assent (check the box "Yes" to participate and print their name) will be required before youth participation is allowed.

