Study Aim 2: Evaluate the feasibility and acceptability of the culturally adapted PEI program. We calculated the frequency of youth attendance rates across sessions, dropout rates, and survey response rates. We also created tabular summaries of the Likert scale ratings from the usability survey and proportion of respondents who rated each module or all modules on average as 2 or 3. A module or the entire program was successfully adapted if at least 80% of youth rated it as a 2 or 3 on the Likert scale for acceptability and enjoyability.

Study Aim 3. Estimate effect size changes in anxiety and depressive symptoms in [tribal name] youth. Primary outcomes of interest for a future efficacy trial will be changes in the RCADS-S scales. For each scale, we computed the change in the scale score from baseline to post-intervention (post – pre) and computed unadjusted averages and standard deviations. A one-sample t-test of the changes in any response scale will have 80% power to detect a standardized effect size (Cohen's d) of at least 0.53, and 90% power to detect an effect size of at least 0.61. We will also obtain adjusted estimates using mixed effects linear regression models of post-test score on pre-test score with demographic factors and random effects for school and intervention group nested within school. This will allow us to estimate intra-class correlations for intervention group and schools, which will be required for sample size estimation in a full efficacy trial.

INSTITUTIONAL REVIEW BOARD AMENDMENTS

The following pages (not numbered, but in order of date) contain tribal college IRB amendments that were submitted and approved throughout the study period.

February 9, 2021

Dear [tribal college] IRB,

We are requesting a minor modification for the approved study titled, "A Native Path to Courage." We have outlined the modification below.

- 1) We plan on using a professional online transcription service (Rev.com) to transcribe work and focus group data. The company uses state-of-the-art encryption procedures for audio files to be uploaded and all professional transcribers are required to sign nondisclosure and confidentiality agreements (<https://www.rev.com/enterprise/security>). In addition, we can request for all audio files to be removed from their servers after transcription is complete. We will remove names from the transcription documents upon receipt. Only first names are mentioned in the audio recordings.

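### Does the 80% usability rule need a fixed denominator, given that the SAP writes of respondents in one sentence and youth in the next?

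*Combined protocol and SAP*

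**What the plan says.** The rule is in the Statistical Analysis Plan for Phase 2, Study Aim 2. The SAP first describes the statistic to be tabulated from the usability survey: the "proportion of respondents who rated each module or all modules on average as 2 or 3". The next sentence sets the criterion: "A module or the entire program was successfully adapted if at least 80% of youth rated it as a 2 or 3", judged on acceptability and enjoyability. The same paragraph also commits to reporting the "frequency of youth attendance rates across sessions, dropout rates, and survey response rates".

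The protocol explains how a rating could be missing. The section on the Phase 2 evaluation says: "The post-adaptation usability survey was administered at the end of each session". The section on the Youth Post-Adaptation Usability Survey confirms that timing. The Phase 2 section also states: "All youth were notified of their right to withdraw the study and intervention at any time without consequence". The Informed Consent part of the data and safety monitoring plan adds that "they can quit at any time or not answer questions without consequence". On numbers, the Phase 2 section reports that "we recruited 28 Native youth ages 8-12 years-old", with 15 per school in brackets.

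**The concern.** Two adjacent sentences use two different words for the denominator. If *respondents* governs, a child who was absent, had withdrawn or skipped the item drops out of that module's percentage. If *youth* means everyone enrolled, the same child stays in the denominator and counts against the module. No section defines *youth* in the rule or says what to do with a missing rating. For the all-modules average, nothing says whether a child who rated only some modules is kept.

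This is the SAP's only success criterion, and the sample is small enough for one child to matter. A module could be called successfully adapted under one reading and not under the other, and a reader of the label alone could not tell which reading had been used.

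**Working it through.** **Inputs.** The cut-off is 80% (SAP, Study Aim 2). It is a chosen value, so there is no derived figure to reproduce. The number enrolled is N = 28 (Phase 2 section). The bracketed 15 per school at two schools gives 2 × 15 = 30 as an alternative. The number unrated, m, is not in the documents, so I take 1 to 3 as an assumption. Each youth is treated as giving one favourable or unfavourable verdict per module.

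**Formula.** The fewest favourable ratings that pass is 0.80 × denominator, rounded up. The denominator is N − m for raters and N for all enrolled. The label differs at any count x where x/(N − m) is at least 80% but x/N is below 80%.

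**N = 28.** All enrolled: 0.80 × 28 = 22.4, so 23 are needed (23/28 = 82.1%; 22/28 = 78.6% fails).

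| Unrated | Raters | 0.80 × raters | Needed | Share of raters | Share of 28 | Counts where the label differs |
|---|---|---|---|---|---|---|
| 1 | 27 | 21.6 | 22 | 81.5% | 78.6% | 22 |
| 2 | 26 | 20.8 | 21 | 80.8% | 75.0% | 21, 22 |
| 3 | 25 | 20.0 | 20 | 80.0% | 71.4% | 20, 21, 22 |

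**N = 30.** All enrolled: 0.80 × 30 = 24 needed. With one unrated, 0.80 × 29 = 23.2, so 24 are still needed and nothing changes. With two unrated, 0.80 × 28 = 22.4, so 23 suffice (23/28 = 82.1% against 23/30 = 76.7%). At 30, at least two unrated youth are required.

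**Which reading the text supports.** Three points favour raters:

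1. Only youth complete the usability survey, so its respondents and its youth are the same people.
2. The rule's verb is *rated*; a child with no rating has not rated the module.
3. The sentence just before defines the tabulated proportion over respondents, and the rule applies a threshold to that proportion.

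**Whether the enrolled denominator would be better.** With six of 28 unrated, the highest possible enrolled result is 22/28 = 78.6%, a failure even if every rater is favourable. It would count absence from an after-school programme (IRB amendment of February 16, 2024) as dislike of the module. That mixes attendance with acceptability, and the SAP already reports attendance separately.

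**The case for a change.** The strongest case for a change is that the rule never states the respondent reading, that missing ratings are foreseeable, and that the attendance and response rates are not set beside each 80% result. An overall response rate would not show whether a particular module's verdict turns on a few unrated children. Naming the denominator and adding the number rated would cost one sentence and a table column. The background section also reports 25% loss in an earlier adapted programme. If that occurred here, 0.25 × 28 = 7 would be unrated, and 17 favourable would be 17/21 = 81.0% of raters but 17/28 = 60.7% of those enrolled.

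Part of this stands. The two words do differ, the counts are correct, and the treatment of partial raters is unstated.

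The rest carries less weight. The 25% figure comes from a programme for youth with a trauma history and post-traumatic stress symptoms, not universal delivery. It describes leaving treatment, not lacking a rating at one session. There is also a separate worry, that children who dislike a module are the ones who go unrated. That is selective non-response, and naming a denominator would not remove it. The documents give no evidence of it, and proportional loss leaves the share unchanged: 21/28 less three favourable and one unfavourable is 18/24, both 75.0%. Reasons for loss could be recovered only in part, because the attendance and dropout record described under Confidentiality holds 0/1 codes against names, without study IDs.

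**Conclusion.** No change to the plan is needed. Read in context, the 80% rule applies among youth who rated the module, which is a sound measure of acceptability. Spelling that out would produce the same verdict as following the SAP as written. The stricter enrolled version would be at most a side display, since it cannot fairly serve as a criterion.

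The possible effect is confined to results near the cut-off. With 28 enrolled and one to three unrated, the label differs only at 20 to 22 favourable ratings; with 30, one unrated youth makes no difference. The rule is descriptive, so no error rate or power figure depends on it. The documents attach no later decision to the label, and post-intervention focus groups and interviews assess acceptability as well.

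What remains is a detail the analyst settles when preparing the tables. For the all-modules result, averaging over the modules a youth actually rated, and keeping every youth with at least one rating, is an ordinary choice that retains early leavers' views. Reporting the number of raters with each percentage is normal practice.

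This conclusion assumes that *youth rated it* means youth who gave a rating. The actual number unrated is not in the documents, so the figures show what could happen, not what did.

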The purpose of this study was to build upon our community-based participatory research (CBPR) partnerships with the [tribal name] tribal community to culturally adapt an evidence-based, indicated PEI program for universal delivery with 8-12-year-olds living on the [tribal name] Reservation using a systemic, theory- and culturally-grounded qualitative approach. In addition, we will use a mixed methods approach to evaluate the feasibility of delivering the adapted PEI in two tribe-serving schools and estimated effect sizes of changes in anxiety and depression from pre- to post-intervention using single-group design (i.e., no control group). We also aimed to determine the extent to which the program was acceptable and enjoyable for [tribal name] youth.

Research Design

Our study involved two major phases:

- 1) a qualitative phase, which included collaboration between the CAB and research team that resulted in a conceptual framework for cultural adaption of the PEI program, gathering suggestions for cultural adaptations and to improve the PEI program from focus groups with key adult stakeholders in the [tribal name] community (Elders, parents, teachers, and mental health specialists) and youth stakeholders, and the CAB making cultural adaptions to the PEI program based on the focus group data.
- 2) a clinical trial phase, which included delivery of the adapted intervention in two tribal serving schools for the [tribal community name] Reservation using a pre-post, single group design (i.e., no control group). We evaluated feasibility and acceptability using youth and provider self-report data and estimated the effect sizes of changes in youth anxiety and depressive disorder symptoms using youth and teacher reports. In addition, we gathered survey data on youth resilience, anxiety control beliefs, and rumination.

Cultural Adaptation of the PEI Program (Phase 1)

Development of Conceptual Framework and Review of the PEI program (Step 1)

In Year 1, the 8-10 member CAB (Elders, parents, teachers, mental health professionals, cultural experts) and research team met once a month and engaged in several activities throughout Step 1 described in this section and Step 3 described in a later section. All CAB members completed a

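### Does standardising by the SD of change make the Aim 3 effect size unusable for planning an efficacy trial?

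*Combined protocol and SAP*

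**What the plan says.** Study Aim 3 of the SAP for Phase 2 sets out four things.

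- **Summary of change.** For each RCADS scale "we computed the change in the scale score from baseline to post-intervention" (post minus pre) and "computed unadjusted averages and standard deviations".
- **Power.** "A one-sample t-test of the changes in any response scale" is given two detectable effects: the first is worded "80% power to detect a standardized effect size (Cohen's d) of at least 0.53"; the second is 0.61, at 90% power. This is the only place in the SAP where Cohen's d appears.
- **Adjusted analysis.** The plan adds "mixed effects linear regression models of post-test score on pre-test score with demographic factors", with random effects for school and for intervention group within school. From these models it will estimate intra-class correlations, the only quantity it describes as needed to size the later trial.
- **Future outcome.** "Primary outcomes of interest for a future efficacy trial will be changes in the RCADS-S scales".

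The Purpose of the Study and Research Design sections of the protocol describe a single-group, pre-post study without controls. Estimating effect sizes for anxiety and depression is one of its purposes.

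**The concern.** A d from a one-sample test of change is standardised by the SD of change. Published between-group effects are usually standardised by the SD of the score. With equal SDs before and after, the two differ by a factor of 1/√(2(1−r)), where r is the pre-post correlation. For r above 0.5, the same change in points gives a larger one-sample d. The SAP does not list the baseline SD, the post SD or r among its summaries, so a reader given only the mean and SD of change cannot convert between the two.

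Aim 3 looks ahead to an efficacy trial. If a planner put the one-sample d into a formula for comparing post scores between two arms, that trial could be much too small, and the pilot's main quantitative result would have misled the planning it was meant to support.

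**Working it through.** **Inputs.** Detectable d of 0.53 (80% power) and 0.61 (90% power), from Study Aim 3. The significance level is not stated; two-sided 5% is assumed. r is not stated; 0 to 0.9 is examined. For the future trial the assumptions are 1:1 allocation, 80% power, equal pre and post SDs, no change in controls, and no clustering or dropout.

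**1. The plan's own figures.** Power of a one-sample t-test from the noncentral t distribution, with 30 youth, two-sided 5%:

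- detectable d is 0.529 at 80% power and 0.612 at 90%;
- power is 80.1% at d = 0.53 and 89.8% at d = 0.61.

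The figures reproduce, so d here is mean change / SD of change, the correct measure for that test. (They match 30 youth, not the 28 that the protocol says were recruited, for whom power is 77.1% and 87.5%. That is a separate matter and does not bear on the standardiser.)

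**2. Where a shortfall of 40% to 60% comes from.** Let S be the score SD.

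- SD of change = S√(2(1−r)), so d in score-SD units = 0.53 × √(2(1−r)).
- n per arm = 2(1.96 + 0.842)²/d² = 15.70/d².
- Using 0.53 directly: 15.70/0.2809 = 55.9, so 56.
- Comparing post scores only at r = 0.7: d² = 0.2809 × 0.6 = 0.1685, so 94 per arm.
- Comparing post scores only at r = 0.8: d² = 0.2809 × 0.4 = 0.1124, so 140 per arm.

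The shortfall is 1 − 2(1−r) = 2r − 1: 40% at r = 0.7 and 60% at r = 0.8. It is 20% at 0.6 and zero at 0.5. Below 0.5 the trial would be too large: 40 per arm would do at r = 0.3, and 28 at r = 0.

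**3. The outcome the SAP names.** If the future trial compares mean change between arms, the outcome's SD is the SD of change. The standardised difference is then 0.53 whatever r is, and n is 56 per arm.

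**4. A baseline-adjusted comparison.** The residual SD is S√(1−r²). The standardised difference is

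0.53 × √(2(1−r)) / √(1−r²) = 0.53 × √(2/(1+r)),

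which is never below 0.53, because r cannot exceed 1.

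| r | Post score only, n per arm | Change score, n per arm | Baseline-adjusted, n per arm | Power of 56 per arm, baseline-adjusted |
|---|---|---|---|---|
| 0.5 | 56 | 56 | 42 | 90% |
| 0.6 | 70 | 56 | 45 | 88% |
| 0.7 | 94 | 56 | 48 | 86% |
| 0.8 | 140 | 56 | 51 | 84% |
| 0.9 | 280 | 56 | 54 | 82% |

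The shortfall therefore appears only in the column for an analysis that ignores baseline.

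**5. Whether the SAP carries d forward.** It does not say so. The 0.53 is a detectable effect for the pilot's own test, not an estimate offered for later use. The mean and SD of change are reported in scale units, and they are the direct inputs for a change-score trial. The post-on-pre models also produce a pre-score slope and a residual variance, which are the inputs for a baseline-adjusted trial.

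**The case for a change.** The best case on the other side is that an aim devoted to effect sizes never states its standardiser. The SAP does not list baseline SD, post SD, correlation or a confidence interval. The protocol's background cites wait-list and treatment-as-usual comparisons, and a d standardised by the SD of change is not on the same scale as effects in score-SD units. Youth and teacher ratings may also have different pre-post correlations, so equal changes in score-SD units could give unequal d values.

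All of that is fair as a reporting point, and the extra statistics would cost little. It does not show that following the plan leads to a wrong result. Both standardisers are recognised, and a preference for the baseline SD does not make the SD of change an error.

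A second point also stands but is a different one. Without controls, mean change includes whatever would have happened without the programme. If controls showed 20% to 30% of the change (an assumption), d would fall from 0.53 to 0.424 or 0.371, and the need would rise from 56 to 88 or 115 per arm. That comes from the single-group design, which the protocol states openly. Dividing by the baseline SD would not remove it.

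**Conclusion.** The concern does not hold. For the change outcome that the SAP names for the future trial, the SD of change is the correct standardiser and the shortfall is 0% at every r. For a baseline-adjusted comparison it is mildly conservative: 56 per arm against 48 to 51 at r = 0.7 to 0.8. An under-sizing of 40% to 60% needs an assumed r of 0.7 to 0.8, a post-score-only analysis that the SAP does not mention, and a use of d that the SAP does not propose. These results assume equal pre and post SDs, no change in controls, and no clustering or dropout. What remains is a suggestion to list a few more descriptive statistics.

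### Aim 3: the t-test power figures fit 30 independent youth, not 28 recruited for delivery in six groups, and no interval for the mean change allows for those groups

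*Combined protocol and SAP*

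**What the plan says.** All of the analysis text is in the SAP, Study Aim 3. It covers three things.

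- **Estimate of change.** "For each scale, we computed the change in the scale score from baseline to post-intervention", and the investigators "computed unadjusted averages and standard deviations". No confidence interval is named.
- **Power.** "A one-sample t-test of the changes in any response scale will have 80% power to detect a standardized effect size" of at least 0.53, and "90% power to detect an effect size of at least 0.61". The sentence gives no sample size, alpha, ICC or dropout allowance. This is the only test named for the change.
- **Mixed model.** Adjusted estimates are to come from a regression of post-test on pre-test score with demographic factors and "random effects for school and intervention group nested within school". The SAP adds: "This will allow us to estimate intra-class correlations for intervention group and schools", for sizing a full efficacy trial.

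The design facts are in the protocol section on the Phase 2 evaluation. There, "we recruited 28 Native youth ages 8-12 years-old", but the same sentence says "15 youth per school) to participate in the adapted PEI program", which makes 2 × 15 = 30. Delivery was to groups of 3 to 5, three groups in each of two schools. The section on post-intervention focus groups also counts 30 youth, as six groups of five.

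**The concern.** Aim 3 is an estimation aim that looks ahead to an efficacy trial, so a statement of precision is central to it. The only precision statement in the plan is the power of a t-test that treats every youth as independent. Youth in one delivery group share a provider, sessions and peers, and the plan itself expects correlation, since it sets out to estimate group and school ICCs. If changes are correlated within groups, 28 youth carry less information than 28 independent observations, and an interval or p-value from the one-sample t-test is too favourable. The power sentence would then promise more than the design delivers, and a later trial could lean on an effect estimate that looks firmer than it is.

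**Working it through.** **1. Reproduce the stated figures.** Power of the one-sample t-test comes from the noncentral t distribution with n − 1 df and noncentrality d√n. Two-sided 5% is assumed.

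| n | d at 80% | d at 90% | power at 0.53 | power at 0.61 |
|---|---|---|---|---|
| 28 | 0.549 | 0.636 | 77.1% | 87.5% |
| 29 | 0.539 | 0.624 | 78.7% | 88.7% |
| 30 | 0.529 | 0.612 | 80.1% | 89.8% |
| 31 | 0.520 | 0.602 | 81.5% | 90.8% |

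For the named test, only n = 30 rounds to both printed values. One-sided 5% matches both at no n from 20 to 35. The normal approximation at n = 28 gives (1.960 + 0.842)/√28 = 0.529 and (1.960 + 1.282)/√28 = 0.613, which also round to 0.53 and 0.61. A basis of 30 is therefore likely but not proven.

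**2. Effect of the six groups on the t-test.** Inputs: n = 28, six groups, sizes taken as 5, 5, 4, 5, 5, 4 (an assumption that fits 3 to 5 per group), total variance 1, no school variance. The group ICC ρ is not in the documents, so 0 to 0.20 is assumed.

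The sum of squared sizes is 4 × 25 + 2 × 16 = 132, so the design effect is 1 + (132/28 − 1)ρ = 1 + 3.714ρ. Its square root is the factor by which the t-test understates the standard error. Type I error at nominal 5% is by simulation.

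| ρ | √(design effect) | type I error, one-sample t | type I error, six group means (5 df) |
|---|---|---|---|
| 0 | 1.00 | about 5% | about 5% |
| 0.05 | 1.09 | about 7% | about 5% |
| 0.10 | 1.17 | about 9% | about 5% |
| 0.20 | 1.32 | about 14% | about 5% |

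**3. Power of an analysis that allows for the groups.** The mean of the six group means has variance [6ρ + (1 − ρ)Σ(1/m)]/36, where Σ(1/m) = 4/5 + 2/4 = 1.3. Power uses noncentrality d/SE with 5 df. The width ratio is the average length of the six-means interval over that of the one-sample t interval.

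| ρ | SE | power at 0.53 | power at 0.61 | d at 80% | width ratio |
|---|---|---|---|---|---|
| 0 | 0.190 | 61% | 73% | 0.67 | 1.21 |
| 0.05 | 0.207 | 54% | 66% | 0.73 | 1.32 |
| 0.10 | 0.222 | 49% | 60% | 0.78 | 1.42 |
| 0.20 | 0.249 | 41% | 51% | 0.88 | 1.61 |

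**4. Teacher ratings.** The teacher RCADS is completed by each child's homeroom teacher, and nothing says that teachers are nested in delivery groups. A simulation with teachers crossing groups within school, two or four teachers per school, teacher ICC 0.10 to 0.20 (all assumed) and no group effect gives a six-means type I error of about 7% to 13%. That is better than the one-sample t-test in the same cases, but not 5%.

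**The case against.** The strongest reply is that clustering is already handled. The SAP promises adjusted estimates from a model with group and school random effects, and gives the ICCs as something the model also allows. That stands: a reader might infer that the plan ignores clustering, or fits the model only for ICCs, and the text supports neither. What remains is narrower. In a single-arm regression of post on pre with demographic factors, no coefficient is the mean change unless the plan defines it so. No interval or small-sample df is attached, and with six groups and two schools that choice matters.

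A second reply is that this is a feasibility pilot and the t-test appears only in a power sentence. That also stands. A reader might infer that inflated type I error could lead to a wrong efficacy decision, but the documents attach no success rule to the test and do not say that its p-value will be reported.

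A third is that 28 against 30 is trivial. It is the smaller part: about 3 percentage points of power, and the normal approximation may explain it. Nor should 28 be read as the number treated, since the protocol says recruited. The assumption of independence matters more whenever the ICC is above zero.

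Finally, recomputing power after recruitment adds little beside an interval. That is fair, and it is why removing the claim is an acceptable alternative to restating it.

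**Conclusion.** The point holds in this limited form and should be fixed. For the named test, the power claim is about 3 points too high at 28 independent youth. An analysis that respects the six groups has 61% power at d = 0.53 and 73% at d = 0.61 even at ICC 0, because it has only 5 df, and 41% and 51% at ICC 0.20. Any standard error from the one-sample t-test would be too small by a factor of about 1.09 to 1.32 at ICC 0.05 to 0.20. At ICC 0 the t-test is valid and only the sample-size discrepancy remains.

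The unadjusted mean change is a sound point estimate. The harm is confined to the power claim and to any precision reported from that test. These figures rest on two-sided 5%, the assumed group sizes and ICC range, no school-level variance and no dropout.

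**What to change.** 1. Reconcile 28 recruited with 15 per school. Restate the power sentence for the actual number in six groups over a stated ICC range (for 28, the third table above), or remove the claim.
2. For each youth-reported RCADS scale, report the mean change with one pre-chosen 95% interval: a t interval on the six group mean changes, 5 df. State that it weights groups equally and does not cover variation across schools, of which there are only two.
3. Keep the mixed model for both of its stated purposes, adjusted estimates and ICCs.
4. For teacher-reported RCADS, note that ratings also cluster by homeroom teacher. Label the six-group interval as possibly too narrow if teachers cross groups.
5. Label any interval for the standardized change as approximate. The SAP describes the change scores in the past tense; if they have already been analysed, disclose the interval as post hoc.

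The cost is a few lines of text and code and no new data. Intervals become about 1.2 to 1.6 times as wide as the one-sample t interval. If the ICC is truly 0, the extra width (1.21 times) is a pure loss.
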